5.5 Method of Assigning Subjects to Treatment Groups

Subjects who have signed the ICF and are enrolled into the study will be entered into the electronic data capture (EDC) system. Subjects will have the same subject identification number in this study as they had in Study ACP-103-032. The subject identification number

consists of a 3-digit site number followed by a unique 3-digit number. Subjects will keep this same subject identification number throughout the study.

5.6 Concomitant Medications

All ongoing concomitant medications will be captured from the preceding double-blind study (ACP-103-032) and will be recorded from Baseline through the EOS/ET visit.

In order to ensure that appropriate concomitant therapy is administered, it is essential that subjects be instructed not to take any medication without prior consultation with the Investigator.

The Investigator may prescribe, adjust, or discontinue appropriate medication to treat or manage AEs. The Sponsor and Investigator will confer to determine whether it is appropriate to continue such a subject in the trial if a prohibited medication is prescribed.

Subjects who take prohibited concomitant medications during the trial will be discontinued, unless the discontinuation presents an unacceptable medical risk. The justification to allow the subject to continue in the trial will be made by the Sponsor with medical input from the Investigator, and will be documented. If allowed to remain in the trial, this will be reported as a major protocol deviation and not a waiver. All follow-up safety assessments must be completed and documented as outlined in the protocol.

5.6.1 Permitted Concomitant Medications

All concomitant antidepressants, cholinesterase inhibitors, memantine, and other permitted medications should remain at a stable dose throughout the study, if possible.

5.6.2 Prohibited and Restricted Medications

Restrictions for concomitant medications should be followed through the EOS/ET visit as specified in [Appendix B](#) and [Appendix C](#). These appendices do not constitute an exhaustive list and any questions regarding prohibited and restricted medications should be discussed with the Medical Monitor or appropriate designee.

Use of medications that could interfere with study conduct or any questions regarding prohibited and restricted concomitant medications should be reviewed and/or discussed with the Medical Monitor or appropriate designee.

Medications that can prolong QT interval are prohibited (or restricted if approved by the Medical Monitor) as specified in [Appendix B](#).

5.6.3 Rescue Medications

At the discretion of the Investigator, lorazepam (a benzodiazepine) may be used as a rescue medication for the management of agitation and/or aggression. Any use or increase in dose of

lorazepam must be documented. At a maximum dose of up to 2 mg per 24-hour period, lorazepam will be allowed as rescue medication only on an intermittent or PRN basis, and should not be taken within 24 hours prior to the next study visit. Lorazepam may not be used for more than 10 cumulative days in any 4-week period. If lorazepam is not available, another intermediate-acting benzodiazepine may be used at doses equivalent to lorazepam doses.

5.7 Blinding

This study will be conducted as an open-label study.

5.8 Investigational Drug Handling

5.8.1 Test Article

Pimavanserin tartrate is a white to off-white powder. Pimavanserin tablets include the active compound (pimavanserin) and the following excipients: [REDACTED]

Pimavanserin will be provided as 10 mg and 17 mg strength tablets.

Pimavanserin used for the tablets are manufactured under current Good Manufacturing Practices compliance by [REDACTED]

5.8.2 Investigational Drug Packaging

Study drug will be supplied as individual uniquely numbered bottles. Each bottle contains 60 tablets and is sufficient for 4 weeks of treatment. Each tablet contains pimavanserin 10 mg or 17 mg.

5.8.3 Receipt of Investigational Drug Supplies

The Investigator and/or study staff is responsible for taking an inventory of each shipment of investigational drug received and comparing it with the accompanying drug accountability report/material shipping form. The Investigator or study staff member will verify the accuracy of the information on the form, sign and date it, and return the form to the Sponsor or designee. All investigational drug supplied is for use in this study only and should not be used for any other purpose.

5.8.4 Storage of Investigational Drug

The investigational drug must be kept at 15°C to 30°C (59°F to 86°F) [see USP Controlled Room Temperature] in a secure area with restricted access and according to applicable country, state, and federal regulations. Neither the Investigator, nor the pharmacist, nor any of his/her designees may provide investigational drug to any person not participating in the study.

5.8.5 Investigational Drug Dosing

Study drug will be dispensed to the subject to take home at the Baseline Visit. The subject and their study partner/caregiver will be provided instructions to take the first dose of study drug on the following day. It is recommended that the subject take the study drug at approximately the same time each day as a single, oral dose. Study drug can be taken with or without food consumption.

At the Week 2 visit (Visit 2) and thereafter, the dose of pimavanserin may be adjusted based on the Investigator's assessment of clinical response (see [Section 5.4](#)). Dose adjustments must be recorded and include date of change, dose, and reason for change. At each visit where drug is dispensed, previously dispensed unused drug and any empty containers are to be returned to the Investigator.

5.8.5.1 Treatment Period

At Baseline, subjects will be provided with study drug to take home. The subject and their study partner/caregiver will be provided instructions to take the first dose of study drug on the following day. It is recommended that the subject take the study drug at approximately the same time each day.

Additional study drug will be provided according to the Schedule of Events and Assessments ([Appendix A](#)) or at unscheduled study visits. Investigational drug supplies will be labeled in accordance with all applicable guidelines and/or regulations.

5.8.6 Record of Dispensing

Accurate recording of all investigational drug administration for individual subjects will be made in the appropriate section of the subject's eCRF as well as in the site investigational drug dispensing and reconciliation form. Drug accountability records must be updated as subjects are enrolled and throughout the conduct of the study.

5.8.7 Accountability

The Investigator or designee will keep current and accurate records of the investigational drug product dispensed, used, and returned for each subject to assure the health authority and Sponsor that the investigational drug is being handled appropriately. Subjects should be instructed to return all packaging, bottles, and unused medication to the Investigator at scheduled and unscheduled clinic visits when drug is dispensed and at the EOS/ET visit.

At appropriate intervals during the study, investigational drug reconciliation will be performed by the Sponsor representative who may return appropriate used and unused investigational drug and used and unused packaging to the Sponsor's designee for destruction.

At the conclusion of the study, final investigational drug reconciliation will be conducted at the site. Final investigational drug accountability documentation will be maintained at both the site and at ACADIA. Any remaining unused investigational drug and all used and unused packaging will be sent back to the Sponsor's designee for destruction. Documentation of investigational drug destruction will be recorded and maintained by both ACADIA and the Sponsor's designee.

6 EFFICACY AND SAFETY ASSESSMENTS

6.1 Efficacy Assessments

The following efficacy endpoints will be assessed in this study using the measures described in this section: CMAI, ZBI, NPI-C, MMSE, mADCS-CGIC, KSS, and ADCS-ADL.

Of the measures listed in the following sections, the CMAI should be completed first, followed by completion of the other instruments. For each scale, the time period assessed will be from the time of the last scheduled assessment. All Baseline assessments that are referred to in the following sections will be carried over from the Week 12 visit of Study ACP-103-032, where applicable.

6.1.1 Cohen-Mansfield Agitation Inventory

The CMAI was developed to assess the frequency of manifestations of agitated behaviors in elderly persons ([Cohen-Mansfield 1989](#); see [Appendix D](#)).

The CMAI is a 29-item scale designed to systematically assess agitation, rated on a 7 point (1-7) scale of frequency. Subjects are rated by their primary caregiver regarding the frequency with which they manifest physically aggressive, physically non-aggressive and verbally agitated behaviors. The CMAI may be self-administered (by a caregiver) or, as in this study, it may be completed by interview. Ratings are inclusive of the 2 or 4 weeks prior to the administration of the scale. Separate scores for agitation and aggression behaviors can be derived from the CMAI in addition to the total score.

The CMAI will be performed at Baseline (Day 1) and at all scheduled clinic visits.

6.1.2 Zarit Burden Interview

The ZBI was designed to assess the stresses experienced by caregivers of patients with dementia ([Zarit et al. 1980](#); see [Appendix E](#)). The ZBI can be self-reported or, as in this study, administered as an interview. Caregivers are asked to respond to a series of 22 questions about the impact of the patient's disabilities on their life. For each item, caregivers are to indicate how often they felt that way (never, rarely, sometimes, quite frequently, or nearly always). The ZBI will be administered at Baseline (Day 1) and at Weeks 2, 4, 8, 12, 20, 28, 36, 44, and 52 (EOS/ET).

Note: Professional caregivers do not complete this form.

6.1.3 Neuropsychiatric Inventory – Clinician Rating Scale

The NPI-C ([de Medeiros et al. 2010](#)) was developed to assess psychopathology in patients with dementia ([Appendix F](#)). The NPI-C evaluates NPS across multiple behavioral domains, as in the NPI ([Cummings et al. 1994](#)), as a standalone measure for specific NPS domains (e.g., dysphoria, agitation), or as a combination of both (presence of NPS across domains plus particular focus on one or more specific domains). The score of each item, if present, is clinically evaluated based on the symptom frequency, severity/intensity, and distress of a behavior. Multiple behaviors within a category are rated and included in the score. The NPI-C version of the NPI scale was designed to be administered by the clinician to the caregiver and can be administered to a professional caregiver or other involved person as long as they have detailed knowledge of the subject's behavior. If a subject is not able to provide reliable information (e.g., due to cognitive impairment, or is uncooperative), the NPI-C should be rated by the clinician using all other available information including behavioral observations.

The complete NPI-C (i.e., all domains) will be performed at Baseline, Weeks 12, 28, and 52 (i.e., Visits 1, 5, 7, and 10 [EOS/ET]). The agitation and aggression domains of the NPI-C alone will be performed at Weeks 2, 4, and 8 (i.e., Visits 2, 3, and 4).

6.1.4 Mini–Mental State Examination

The MMSE is a brief 30-point questionnaire that is used to quantitatively assess cognition ([Folstein et al. 1975](#); see [Appendix G](#)). The MMSE includes simple questions and problems in a number of areas: the time and place of the test, repeating lists of words, arithmetic, language use and comprehension, and copying a drawing. It can be used to screen for cognitive impairment, to estimate the severity of cognitive impairment at a given point in time, to follow the course of cognitive changes in an individual over time, and to document an individual's response to treatment. The MMSE will be administered at Baseline (Visit 1) and at Weeks 4, 8, 12, 20, 28, 36, 44, and 52 (i.e., Visits 3, 4, 5, 6, 7, 8, 9 and 10 [EOS/ET]).

6.1.5 Modified Alzheimer's Disease Cooperative Study - Clinical Global Impression-Change

The mADCS-CGIC scale ([Schneider et al. 1997](#)) will be used to allow the Investigator to determine the subject's overall clinical condition as it relates to their symptoms of agitation and aggression, and to address the clinical significance of changes from Baseline in other psychometric measures ([Appendix H](#)). The mADCS-CGIC interview will be performed by the Investigator or a medically qualified rater. After completion of the interview, the rater will be asked to rate the subject's symptoms of agitation and aggression relative to the Baseline

interview from the parent study (ACP-103-032), using a standardized 7-point scale (1=marked improvement to 7=marked worsening).

The mADCS-CGIC will be administered at Baseline (Visit 1) and at all scheduled clinic visits.

6.1.6 Alzheimer's Disease Cooperative Study - Activities of Daily Living Inventory

The ADCS-ADL is an inventory to assess activities of daily living in subjects with AD (Galasko et al. 1997; see Appendix I). This is a caregiver-rated questionnaire that includes 23 items related to subject ADLs. The instrument assesses functional capacity across a large spectrum of dementia severity. The ADCS-ADL will be administered at Baseline (Visit 1) and at Weeks 12, 28, and 52 (i.e., Visits 5, 7, and 10 [EOS/ET]).

6.1.7 Karolinska Sleepiness Scale

The KSS is a self-reported subjective measure of a subject's level of drowsiness (Akerstedt and Gillberg 2009; Johns 2009; see Appendix J). With the modified version (Geiger Brown et al. 2014) respondents must choose which of 9 statements most accurately describes their level of sleepiness over a period of time, which for this study will be “on average over the previous week” (see Appendix J). The KSS will be administered at Baseline (Visit 1) and at Weeks 12, 28, and 52 (i.e., Visits 5, 7, and 10 [EOS/ET]).

6.2 Safety Assessments

Standard clinical evaluations and objective measures will be employed to monitor and assess safety during the conduct of this trial. Results of safety assessments will be used to identify any investigational drug-related effects or trends after the trial is completed. Furthermore, results of the safety assessments will be used during the conduct of the trial to monitor and protect the safety of enrolled subjects. Information regarding safety monitoring can be found in the sections below.

Safety and tolerability assessments for all subjects will include: medical and medication history including AD history, physical examinations, vital signs, weight, ECGs, suicidal ideation and behavior, and safety laboratory evaluations.

All Baseline assessments that are referred to in the following sections will be carried over from the Week 12 visit of Study ACP-103-032, where applicable.

6.2.1 Medical and Medication History

Medical and medication history will be carried over from the preceding double-blind study (ACP-103-032).

6.2.2 Alzheimer's Disease History

A thorough subject history specific to their diagnosis of probable AD will be carried over from the preceding double-blind study (ACP-103-032).

6.2.3 Physical Examinations

Physical and neurological examinations will be conducted at Baseline (Visit 1) and Weeks 12 and 52 (i.e., Visits 5 and 10 [EOS/ET]). The examinations may include a review of all body systems (urogenital examination is required only if indicated) and should include a neurological examination (e.g., level of consciousness, speech, cranial nerves [including pupil equality and reactivity], motor assessment, sensory assessment, coordination, gait, reflexes, and Romberg test).

6.2.4 Vital Signs

Vital signs (sitting [at least 3 minutes] blood pressure, pulse, respiratory rate, and temperature) will be performed at Baseline (Visit 1) and at all scheduled visits.

6.2.5 Weight

Weight will be measured at Baseline (Visit 1) and at all scheduled visits.

6.2.6 Electrocardiograms

A 12-lead ECG (single recording) will be performed at Baseline (Visit 1) and at Weeks 4, 12, 28, and 52 (i.e., Visits 3, 5, 7, and 10 [EOS/ET]).

6.2.7 Safety Laboratory Evaluations

Safety laboratory evaluations will be analyzed by a Central Laboratory. Blood and urine samples for safety laboratory evaluations will be collected at Baseline (Visit 1) and Weeks 4, 12, 28, and 52 (i.e., Visits 3, 5, 7, and 10 [EOS/ET]).

Females of child bearing potential must agree to use a clinically acceptable method of contraception (e.g., oral, intrauterine device [IUD; diaphragm], injectable, transdermal or implantable contraception) or abstinence during the study, and 1 month following the last dose of study medication. Abstinence as a method of contraception defined as refraining from heterosexual intercourse during the entire period of risk associated with the study treatments. This option is usually made for a specific moral, religious, legal, or health reason. If heterosexual intercourse does occur, an appropriate method of birth control is required. For all female subjects of childbearing potential, a urine pregnancy test will be performed at Baseline (Visit 1) and at Weeks 4, 12, 20, 28, 36, 44, and 52 (i.e., Visit 3, 5, 6, 7, 8, 9, and 10 [EOS/ET]). Pregnancy tests must be negative at Baseline for study entry and at the Weeks 4, 12, 20, 28, 36, and 44 visits to continue in the study.

Note: A urinalysis is not applicable for those subjects who are unable to provide a urine sample (e.g., incontinent subjects). The reason for not completing the urine sample will be documented.

The laboratory evaluations will include, but not be limited to, the following:

- Clinical Chemistry Serum Tests
 - Sodium (Na), potassium (K), chloride (Cl), phosphorus (P), calcium (Ca), carbon dioxide (CO₂), blood urea nitrogen (BUN), creatinine (CR), uric acid
 - Alanine aminotransferase (ALT/SGPT), aspartate aminotransferase (AST/SGOT), gamma-glutamyl transpeptidase (GGT), alkaline phosphatase (ALP), total bilirubin (TBIL), lactate dehydrogenase (LDH)
 - HbA1c, glucose
 - Albumin (ALB), total protein
 - Prolactin
 - Creatine kinase (CK)/creatinine phosphokinase (CPK)
 - Lipid panel
 - Total cholesterol, HDL-cholesterol, triglycerides, LDL-cholesterol, Cholesterol/HDL ratio, Non-HDL cholesterol
- Hematology Tests
 - Complete blood count (CBC) including
 - White blood cell (WBC) count
 - Complete differential (relative and absolute)
 - Hematocrit (Hct), hemoglobin, red blood cells (RBC), platelets
 - Reticulocytes
- Urinalysis
 - Blood, RBCs, WBCs, protein, glucose, ketones, specific gravity, pH
 - Urine pregnancy test for women with child-bearing potential.

Note: Urinalysis requirement is not applicable to subjects who are unable to provide a urine sample (i.e., incontinent subjects).

Blood samples will be taken during the study for routine safety tests (safety laboratory samples) (~4 total blood draws), as presented in [Table 6–1](#) and detailed in the laboratory manual.

Table 6–1 Safety Laboratory Evaluations

Visit	Tests*
Baseline	CHEM, CBC, UA , and urine pregnancy
Weeks 4, 12, 28, and 52 (EOS/ET)	CHEM, CBC, UA
Weeks 4, 12, 20, 28, 36, 44, and 52 (EOS/ET)	Urine pregnancy

Abbreviations: CBC=complete blood count; CHEM=serum chemistry; EOS/ET=end of study/early termination; UA=urinalysis

* Urinalysis requirement not applicable to subjects who are unable to provide urine sample (i.e., incontinent subjects).

Additional safety testing may be performed at the discretion of the Investigator or designate.

6.2.8 Clinically Significant Abnormalities

Laboratory abnormalities judged by the Investigator to be clinically significant will be repeated as clinically appropriate. Abnormal laboratory test results that are considered to be clinically significant by the Investigator must be recorded as an AE.

Further details on blood and urine sample collection are specified in the laboratory manual.

6.2.9 Suicidal Ideation and Behavior

The Global Clinician Assessment of Suicidality (GCAS) will be used to assess the occurrence of treatment-emergent suicidal ideation and behavior.

The GCAS is a clinician-rated, 5-point scale that is designed to rate the subject’s suicidality based on the report of the subject, the report of the study partner/caregiver, and the clinician’s global assessment. Ratings can be 0 (Absent), 1 (Feels life is not worth living), 2 (Wishes he/she were dead or any thoughts of possible death to self), 3 (Suicidal ideas or gesture), or 4 (Attempt at suicide). The Investigator will record a subject rating, a partner/caregiver rating, and a clinician rating. For a rating of 3 or 4 based on the clinician’s assessment, the date of event will be recorded. At each visit, suicidality since the previous visit will be assessed.

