3 STUDY DESIGN

3.1 Overall Study Design

This study is an open-label extension study of the safety and tolerability of pimavanserin for the treatment of agitation and aggression in subjects with probable AD ([McKhann et al. 2011](#)). This study will be conducted as a 52-week, open-label, flexible-dose extension of Study ACP-103-032. Subjects in Study ACP-103-033 must have completed ACP-103-032 and must meet eligibility criteria.

Study ACP-103-033 subjects **must be** consented prior to the final procedures being performed for Study ACP-103-032 at Week 12. Procedures from the Week 12 visit of Study ACP-103-032 will be carried over to the ACP-103-033 study to be included as baseline information and this visit will be considered the Baseline Visit (Visit 1) of the ACP-103-033 study.

Study periods:

- Open-label treatment period (Baseline through 52 weeks of treatment)
- Safety follow-up period (~30 days after the last dose of study drug)

Treatment Period (Baseline through Week 52)

All subjects will receive once daily (QD) doses of pimavanserin (active study drug) over 52 weeks of treatment, starting with 20 mg a day. At the Week 2 visit, the pimavanserin 20 mg dose may be increased to 34 mg a day based on the Investigator's assessment of clinical response. The Investigator may then adjust the dose from 20 mg to 34 mg or from 34 mg to 20 mg at any visit based on clinical response. A dose change at a time other than at a scheduled clinic visit will require an unscheduled visit to dispense the appropriate dose of study drug. Unscheduled clinic visits may occur as needed.

During the Treatment Period, clinic visits will be conducted at Baseline and Weeks 2, 4, 8, 12, 20, 28, 36, 44, and 52, or upon early termination (ET) from the study.

It is recommended that the study drug be taken at approximately the same time each day.

Doses of concomitant or over-the-counter medications should not exceed those indicated for Permitted and Prohibited Concomitant Therapy and Rescue Medication (see [Section 5.6](#)).

Follow-up of Study Completers

A follow-up safety assessment will be conducted via telephone approximately 30 days after the last dose of study drug for subjects who complete the 52-week treatment period and for those who discontinue prematurely from the study.

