APPENDIX A SCHEDULE OF EVENTS AND ASSESSMENTS

Visit Number	Treatment Period											Follow-Up
	Baseline ^b	2	3	4	5	6	7	8	9	(EOS/ET)	Unscheduled	11
	1	Week 2	Week 4	Week 8	Week 12	Week 20	Week 28	Week 36	Week 44	Week 52		Week 56
Allowable visit window (# days)		±3	±3	±3	±3	±7	±7	±7	±7	+7		+7
Informed consent ^b	X											
Inclusion/exclusion criteria	X											
Physical examination	X				X					X		
Vital signs	X	X	X	X	X	X	X	X	X	X	X	
Weight	X	X	X	X	X	X	X	X	X	X		
ECG ^c	X		X		X		X			X		
Clinical laboratory tests	X		X		X		X			X		
Pregnancy test ^d	X		X		X	X	X	X	X	X		
CMAI	X	X	X	X	X	X	X	X	X	X	X ^h	
ZBI	X	X	X	X	X	X	X	X	X	X		
NPI-C (all domains)	X				X		X			X		
NPI-C (agitation and aggression domains only)		X	X	X								
MMSE	X		X	X	X	X	X	X	X	X		
KSS	X				X		X			X		
mADCS-CGIC	X	X	X	X	X	X	X	X	X	X	X ^h	
ADCS-ADL	X				X		X			X		
Assessment of concomitant medications/procedures	X	X	X	X	X	X	X	X	X	X	X	X
Assessment of AEs ^e	X	X	X	X	X	X	X	X	X	X	X	X
GCAS	X	X	X	X	X	X	X	X	X	X	X	X
Dispense study drug ^f	X ^g	X	X	X	X	X	X	X	X	X	X ^h	
Study drug accountability		X	X	X	X	X	X	X	X	X	X ^h	

Abbreviations and footnotes on next page.

Abbreviations: ADCS-ADL=Alzheimer's Disease Cooperative Study–Activities of Daily Living; AE(s)=adverse event(s); CMAI=Cohen-Mansfield Agitation Inventory; ECG=electrocardiogram; EOS/ET=end-of-study/early termination; GCAS= Global Clinician Assessment of Suicidality; KSS=Karolinska Sleepiness Scale; mADCS-CGIC=modified Alzheimer's Disease Cooperative Study – Clinical Global Impression of Change; MMSE=Mini-Mental State Examination; NPI-C=Neuropsychiatric Inventory-Clinician rating scale; ZBI=Zarit Burden Interview

- ^a Study visits are designated by weeks and have a ± 3 -day window (Visits 2 through 5), or a ± 7 -day window (Visit 6 through 9), or a +7-day window (Visits 10 and 11) calculated from the Baseline Visit.
- ^b Study ACP-103-033 subjects **must be** consented prior to the final procedures being performed for Study APC-103-032 at Week 12. Procedures from the Week 12 visit of Study ACP-103-032 will be carried over as baseline information, if applicable.
- ^c A single 12-lead ECG can be performed any time before blood sampling or at least 30 minutes after blood sampling during clinic visits.
- ^d A urine pregnancy test should be performed for female study subjects of childbearing potential.

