- ^e Any untoward medical occurrence that occurs after the completion of procedures at the Week 12 visit in double-blind Study ACP 103-032 should be recorded as an AE, even if dosing for ACP-103-033 has not begun.
- ^f Study drug will be dispensed to the subject at either scheduled or unscheduled visits.
- ^g Study drug will be dispensed to the subject to take home at the Baseline visit. The subject and their study partner/caregiver will be provided instructions to take the first dose of study drug on the following day.
- ^h To be completed at unscheduled visits where there is a dose change.

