5.3.1 Unscheduled Assessments

Both scheduled and unscheduled assessments, including early termination visits, will be considered for planned timepoint summaries. All assessments will be presented in data listings.

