5.3.2 Multiple Measurements within Visit Windows

If more than one assessment falls within a given window then the assessment closest to the target study day will be selected for the by-visit summaries. If two assessments are equidistant from the target day then the chronologically last assessment will be used for summary. Exceptions may be made for incomplete assessments, in which case, more complete assessments may be given priority. Details are provided in a separate programming conventions document.

For safety summaries where the most extreme values should be selected, e.g. overall post-Baseline minimum, overall post-Baseline maximum and potentially clinically important values for overall post-Baseline summaries, all non-missing post-Baseline values should be considered, regardless of whether the value is selected for the by-visit summaries. All results will be presented in data listings.

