14.6 Other Safety Variables

14.6.1 Suicidal Ideation and Behavior

GCAS is assessed at Baseline, Weeks 2, 4, 8, 12, 20, 28, 36, 44, 52/ET and Follow-up (if applicable) visits.

The number and percentage of subjects for each GCAS rating (0-4) based on clinician's assessment will be tabulated by visit, using the number of subjects with non-missing GCAS score for the given visit and double-blind treatment group as the denominator for the percentages. The number and percentage of subjects reporting any post-Baseline GCAS score of 3 or 4 based on clinician's assessment will also be tabulated, using the number of subjects with at least 1 post-Baseline GCAS score for the given double-blind treatment group as the denominator for the percentages.

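### The by-visit GCAS table keeps one rating per window although each rating covers its own interval, so a displaced rating of 1 or 2 reaches no summary table

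*Protocol*

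**What the plan says.** Protocol 6.2.9 defines the recall period: "At each visit, suicidality since the previous visit will be assessed". SAP 5.2.8 repeats it. GCAS is rated at every scheduled visit, at Week 52 or ET (Protocol 3.4.8), at unscheduled visits (3.4.9) and at the 30-day telephone follow-up (3.4.10). Section 3.4.9 ties the CMAI and mADCS-CGIC to a dose change but sets no such condition for GCAS. Unscheduled visits are built into the design; Protocol 3.1 states: "A dose change at a time other than at a scheduled clinic visit will require an unscheduled visit".

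SAP 5.3.1 pools the ratings: "Both scheduled and unscheduled assessments, including early termination visits, will be considered for planned timepoint summaries". When several fall in one window, SAP 5.3.2 says "the assessment closest to the target study day will be selected for the by-visit summaries", and on ties "If two assessments are equidistant from the target day then the chronologically last assessment will be used for summary". It allows exceptions for incomplete assessments. Separately, it requires safety summaries of extreme values to use all post-Baseline data.

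SAP 14.6.1 plans two GCAS tabulations. Ratings 0-4 are "tabulated by visit, using the number of subjects with non-missing GCAS score for the given visit" and treatment group. Subjects with any post-Baseline clinician rating of 3 or 4 are also counted. No highest-in-window rule is given, and no overall count covers ratings of 1 or 2.

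**The concern.** For a point-in-time measure such as weight, the value nearest the target day is a fair stand-in for others in the window. For a rating of what happened since the last visit it is not, because two ratings in one window describe different stretches of time.

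For example, suppose a Week 20 visit on day 141 is rated 0, and an ET visit on day 160 is rated 2 for the time since day 141. Both lie in the 113-168 window, at distances 0 and 19 from the target of 141, so day 141 is kept. If the last dose was also on day 160, a 30-day call falls on day 190, inside 169-224, and is labelled OL Week 28. The table then shows a rating from before withdrawal and an off-drug telephone rating, but not the rating made at withdrawal.

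GCAS is a named safety endpoint (Protocol 2.1.3), and its by-visit table is the only planned summary of ratings 1 and 2.

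**Working it through.** The plan states no figure on this point, so there is none to reproduce. The check applies the SAP rule to visit calendars.

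**Inputs from the documents**
- Targets and windows, SAP Table 4: 15 (2-21), 29 (22-42), 57 (43-70), 85 (71-112), 141 (113-168), 197 (169-224), 253 (225-280), 309 (281-336), 365 (337-379), 395 (380 onward).
- Visit tolerances, Appendix A: ±3 days (Visits 2-5), ±7 days (Visits 6-9) and a +7 "day window (Visits 10 and 11) calculated from the Baseline Visit".
- Subjects are told to "take the first dose of study drug on the following day", so a visit held exactly on schedule falls on target minus 1.

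**Assumed:** unscheduled and ET days uniform over days 2-363, unless stated otherwise. Leaving out the eight scheduled days gives 362 - 8 = 354 possible days.

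**1. ET rating displaced by the scheduled visit already made in its window**
- Visits on target: every later day in the window loses. Days from target to window end are 6 + 13 + 13 + 5×27 = 167. 167/354 = 47%, or 167/363 = 46% of all days to day 363.
- Visits on target minus 1: an ET visit on target wins on distance, and one on target plus 1 wins the tie. Each of the eight windows loses one day fewer: 167 - 8 = 159, and 159/354 = 45%.
- Visits spread over the tolerance (200,000 simulated calendars): 40% (32% for ET by day 84, 42% after).
- ET visit 7 days after stopping, with no scheduled visit in between: some ET visits move into the next window and survive. Visits on target: 0 + 7 + 7 + 5×21 = 119 of 362 stop days, or 33%. With the tolerance, about 30%. A longer gap lowers it further: at 14 days, 5×14 = 70 of 362, or 19%.

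**2. ET rating also displaced by the follow-up call**
- Take ET on the last dose day, *e*, and the call on *e* + 30. In the 113-168 window the call is nearer or tied when *e* + 30 - 141 ≤ 141 - *e*, so *e* ≤ 126. That is 14 days (113-126), and likewise in the next three windows. In 337-379 it is 13 days (337-349). In the earlier windows it is none.
- Added loss: 4×14 + 13 = 69. Total 167 + 69 = 236, and 236/354 = 67% with visits on target.
- With the tolerance and 0-14 days from last dose to ET visit: 56-62%. With exponential dropout: 55%.
- The call reaches the OL Follow-up window (day 380 on) only if *e* ≥ 350: 14 of 362 days, or 4%.

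**3. Unscheduled rating not selected**

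| Scheduled visits | Not selected |
|---|---|
| All on target | 354/354 = 100% |
| All on target minus 1 | 354 - 8×2 = 338; 338/354 = 95% |
| Spread over tolerance | 84-88% |
| Tolerance, 10% / 20% / 30% missed | 79% / 70% / 61% |

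**4. Scale, by illustration.** With at most 111 subjects, an assumed 30-50% dropout and one ET rating each, displaced ET ratings number between 111×0.30×0.40 = 13 and 111×0.50×0.62 = 34. Only those rated above the kept value would change a window's worst rating.

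**The case against.** Much of the opposing case stands.

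- **Suicidal events are not lost.** A reader might infer that ideation or attempts vanish from the report. They do not: any post-Baseline 3 or 4 is counted under SAP 14.6.1, SAP 5.3.2 keeps all values for extreme-value summaries, and every assessment is listed. The loss is limited to ratings of 1 or 2 and the visit placement of 3 or 4, in a descriptive table.
- **Differing tables are intended.** A displaced 3 would appear overall but at no visit. SAP 5.3.2 allows for this, and the laboratory, vital-sign and ECG tables share the design. It is not an error in itself.
- **Bias towards 0 is not shown.** One might infer that displaced ratings are the worse ones. No section says so. Protocol 4.2 lists withdrawal for living-situation change, non-compliance, withdrawn consent and sponsor discretion. Unscheduled visits may be for dose changes in either direction. Only the direction of possible error follows from the rule: a displaced rating can lower a window's worst recorded value and never raise it.
- **The meaning of previous visit matters.** If sites read it as the previous scheduled visit, a later scheduled rating still covers an unscheduled visit before it, and that half weakens. Protocol 6.1 uses the scheduled wording for the efficacy scales; the GCAS text does not. An ET rating made after the kept scheduled visit is lost on either reading.
- **A highest-in-window rule is imperfect.** It does not align recall with windows: a day-170 rating may mostly describe Week 20 time yet count as Week 28. A maximum-rating table recovers the elevated ratings more simply, so it belongs in the fix.

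SAP 5.3.2 also refers to a separate programming conventions document, which was not available. The SAP mentions it in connection with incomplete assessments, not GCAS.

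**Conclusion.** The point holds for the by-visit GCAS table. As written, the rule leaves out about 61-100% of unscheduled ratings and about 30-47% of ET ratings, the latter rising to 55-67% overall if the follow-up call competes in the same window. These shares rest on assumed visit timing: uniform or exponential ET days, uniform unscheduled days, 0-30% of scheduled visits missed, and, for the lower ET bound, an ET visit within 7 days of stopping. Longer gaps reduce the ET share.

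The effect on the tabulated percentages cannot be sized, because the documents give no dropout rate, unscheduled-visit rate or GCAS distribution. The primary endpoint is untouched, and no hypothesis test is planned. This is a cheap improvement to a safety table and does not threaten the study's conclusions.

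**What to change.** In SAP 14.6.1:

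1. State that the by-visit GCAS table uses the highest clinician rating among scheduled, unscheduled and ET ratings in the window, in place of the closest-to-target rule in SAP 5.3.2.
2. Assign the 30-day follow-up rating to the Follow-up row whatever its study day, so that it neither displaces an ET rating nor appears as a treatment week.
3. Add a table of each subject's maximum post-Baseline clinician rating (0-4) by double-blind treatment group and overall.

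The cost is a few SAP sentences and minor programming, with no new data. By-visit rates may rise slightly, and subjects with more visits get more chances of a high rating; a table footnote should say so.
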